#### **Haemostatic response during major surgical interventions**

The endpoint of assessment of haemostatic effect during major surgical intervention (excellent, good, moderate or none) will be summarised and listed.

#### **Change from baseline till end of trial in treatment satisfaction (Hemo-SAT)**

Data will be scored according to established scoring algorithms (where applicable) and changes from first assessment (at screening/V1) to last assessment (at EoT visit) will be summarised and listed using descriptive statistics. Further analysis will be performed separately by Novo Nordisk Health Economics Department.

### **10.3.3 Exploratory endpoint**

#### **Incidence of anti-N8-GP binding antibodies**

Number of positive/negative samples will be summarised by visit and listed.

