a.	Transferred from previous trial by sponsor. Note that FVIII recovery cannot be transferred and must be sampled. Date of birth will not be transferred.
b.	Demography consists of date of birth and age (unless not allowed according to local regulation, see Appendix 8 ), ethnicity and race (unless not allowed according to local regulation, see Appendix 8 ).
c.	Training must take place at visit 1 and whenever needed afterwards.
d.	Sampling for FVIII activity and antibodies should be scheduled to allow for a wash out of approximately 3 days. Post-dose FVIII activity must be collected 30± 10 min at visits including administration of trial product.
e.	Post-dose FVIII activity and Lupus anticoagulant should be collected if reduced effect of N8-GP or FVIII inhibitor development is suspected.
f.	Lupus anticoagulant sample only.
g.	Will be transferred from previous trial. Patients who have turned 17 years during their participation in NN7088-3859 (pathfinder2) or NN7088-3885 (pathfinder5) will have to fill in the questionnaire.
h.	For patients > 18 years of age, height will only be assessed at visit 1, 5 and EoT.
i.	For selected countries, and if permitted by local regulations, the investigator may offer to send trial product and auxiliaries to the patient's home by courier service. The bodyweight and height may be re-used from the previous visit. For these patients visit 2, 4, 6 and 8 may be conducted as a phone visit.
j.	Only applicable for patients, who have signed the informed consent for Human biological specimen for long term storage. Patients < 12 years will only have blood samples taken, if maximum limit for blood sampling is not exceeded (  ).
k.	In case of severe allergic reactions see section 9.8.8.3

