#### 4.1.3 Exploratory objectives

- To investigate the incidence of antibodies other than inhibitors

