#### **4.2.3 Exploratory endpoints**

- Incidence of anti-N8-GP antibodies
- Incidence of anti-PEG antibodies

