#### **Safety analysis set**

All patients enrolled in the trial have previously been exposed to trial product and therefore all enrolled patients will be included in the Safety Analysis Set. The trial patients will be analysed according to the received treatment.

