#### 10.3.1 Primary endpoint

##### Number of adverse events reported

All reported AEs will be considered treatment emergent adverse events since all patients had been treated with N8-GP in other pathfinder trials prior to participation in this trial. All AEs, serious adverse events (SAEs) and adverse events of special interest (AESIs) will be summarised by frequency of events and frequency of patients with any event. Furthermore, all AEs will be summarised by severity and causal relation to trial product. In addition, listings will be provided displaying all AEs, SAEs and AESIs.

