#### **Incidence of anti-PEG binding antibodies**

Number of positive/negative samples will be summarised by visit and listed. Furthermore, plots will be created of incremental recovery according to PEG antibody status at baseline and during the trial. Rules for exclusion of FVIII activity measurements are as defined in the paragraph on: "Pre-dose FVIII activity levels on N8-GP prophylaxis".

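### The anti-N8-GP and anti-PEG endpoints are named as incidence, but the only planned table counts positive samples by visit, which is prevalence

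*Protocol*

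**What the plan says.** The single exploratory objective (Protocol section 4.1.3) is "To investigate the incidence of antibodies other than inhibitors". It is served by two endpoints in Protocol section 4.2.3: "Incidence of anti-N8-GP antibodies" and "Incidence of anti-PEG antibodies".

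The analysis is in Protocol section 10.3.3 and is repeated in SAP section 2.3.3. For each antibody it reads: "Number of positive/negative samples will be summarised by visit and listed". For anti-PEG one output is added: "plots will be created of incremental recovery according to PEG antibody status at baseline and during the trial".

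Two other statements bear on what such a count means. The safety analysis set definition says: "All patients enrolled in the trial have previously been exposed to trial product". Section 10.3.1 likewise says that "all patients had been treated with N8-GP in other pathfinder trials prior to participation in this trial". The flowchart marks the visit 1 antibody entry with the footnote "Transferred from previous trial by sponsor", so a baseline result is meant to be available for each patient.

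For these two antibodies, neither document defines a set of patients negative at baseline, a new positive, a rule that each patient counts once, or a patient or person-time denominator.

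**The concern.** Incidence asks how many patients who did not have the antibody acquire it during the trial. A by-visit count of positive samples asks how many have it at that moment. The two agree only in a special case, set out under the working. With earlier exposure in every patient, that case cannot be taken for granted.

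The protocol handles comparable outcomes at patient level. Section 9.8.8.1 counts a patient with repeated positive inhibitor tests once, and section 10.3.2.1 reports the number of inhibitor patients. Section 10.3.1 summarises adverse events both as events and as patients with any event. The two binding-antibody endpoints have no patient-level summary.

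At stake is the reading of the immunogenicity results. A report that follows the plan exactly could present prevalence under the name of incidence. Readers could take antibodies carried in from the earlier trials for emergent ones. A steady count could also hide new cases that are balanced by losses.

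**Working it through.** **Plan's own figure.** No figure is stated for the antibody endpoints. The only sample-size figure, the 0.02 upper bound for an unobserved adverse event in 150 patients, reproduces (1 − 0.05^(1/150) = 0.0198; 3/150 = 0.0200) but does not bear on this point.

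**Definitions.** Let N be the number of patients, C the number positive at baseline, L the baseline positives who have become negative by a given visit, E the baseline negatives who are positive at that visit, and S the baseline negatives with at least one post-baseline positive. With one sample per patient per visit and none missing:

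- by-visit proportion = (C − L + E) / N
- incidence proportion = S / (N − C)

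At the last visit these coincide in general only if nobody is positive at baseline (C = 0) and every new positive is still positive (E = S).

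**Inputs.** N = 170 is the expected number assigned to trial product (Protocol section 5.2). Every antibody count below is hypothetical, because the documents give none. No dropout is assumed.

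| Case | Positive at baseline | Reverting | Newly positive | By-visit proportion at last visit | Incidence |
|---|---|---|---|---|---|
| a | 10 | 0 | 0 | 10/170 = 5.9% | 0/160 = 0% |
| b | 0 | 0 | 5, persisting | 5/170 = 2.9% | 5/170 = 2.9% |
| c | 10 | 0 | 5, persisting | 15/170 = 8.8% | 5/160 = 3.1% |
| d | 20 | 0 | 5, persisting | 25/170 = 14.7% | 5/150 = 3.3% |
| e | 20 | 10 | 10, persisting | 20/170 = 11.8% | 10/150 = 6.7% |

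Only case b gives the same answer both ways. In cases a, c and d a baseline row of the table would hint at carry-over. In case e it would mislead, because the count is 20 at baseline and 20 at the end although 10 patients are new.

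**Same table, different incidence.** Suppose the table shows 5 positives out of 170 at baseline and at each of four later visits. Four is an assumption: V3, V5, V7 and EoT are the later assessment visits named in Protocol section 9.

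- Five baseline carriers who stay positive: S = 0, incidence 0/165 = 0%.
- Five baseline carriers who all revert before the first later visit, then five different patients transiently positive at each later visit: S = 5 × 4 = 20, incidence 20/165 = 12.1%.

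The second pattern is extreme, but the planned table is identical in every row. The by-visit counts alone therefore do not determine incidence.

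**Denominators.** Protocol section 5.2.1 lets patients complete early once N8-GP is on the market in their country. The number of positives can then fall between visits without any patient losing the antibody.

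**The case against.** The strongest reply is that the output is more than a count. The results are also listed, and with a transferred baseline result for each patient, new positives, carry-over and losses can be separated by hand. That is correct: the information is not lost. It does not supply the named endpoint, because who is at risk and how each patient is counted would be decided after the results are seen.

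Second, baseline status is not ignored for anti-PEG, since the recovery plots are split by it. This also stands. It shows that the sponsor expects some baseline positivity to be possible, but the status is used for a plot of FVIII recovery and not for the endpoint. Anti-N8-GP has no counterpart.

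Third, these are exploratory, descriptive endpoints without a hypothesis or decision rule, while inhibitors, which do carry treatment consequences, have a proper patient-level rule. This is right and limits the weight of the point.

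Two stronger readings are tempting and should be resisted. A reader might infer that persistent carriers are counted again and again, for example that 17 carriers over five visits would appear as 17 × 5 = 85 positives. The plan summarises by visit and nowhere proposes adding visits together; such a table would show 17 at each visit. Within a scheduled visit a patient normally gives one sample, although unscheduled inhibitor sampling also includes both antibodies (Protocol Appendix 2) and could add some. A reader might also infer that antibodies present at entry persist throughout. Neither document says so; earlier exposure only makes baseline positivity possible.

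**Conclusion.** The mismatch holds. The objective and both endpoints ask for incidence. The only prespecified tabulation gives point prevalence in previously exposed patients, and no incidence summary is planned in either document.

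The size of the discrepancy cannot be stated, because it depends on baseline positivity, new positivity and reversion, for which the documents give no figures. The illustrations run from no difference (nobody positive at baseline, new positives persisting) to a table that fits anything from 0% to 12.1%. They assume 170 patients, complete sampling and, for the last figure, four post-baseline visits.

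This is a minor point. It concerns the specification of two descriptive endpoints and has no bearing on the primary endpoint or the sample size.

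**What to change.** In Protocol section 10.3.3 and SAP section 2.3.3, for each of the two antibodies:

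- State which result is the baseline (the transferred visit 1 result) and how a missing one is handled.
- Report the number and proportion of patients with at least one post-baseline positive among those negative at baseline, each patient counted once as is done for inhibitors. An exact 95% confidence interval is preferable but not essential.
- Show patients positive at baseline separately, for example as still positive or no longer positive.
- Keep the by-visit table and the listing, and label the table as prevalence.

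The cost is a few lines of text and one extra patient-level table covering both antibodies. It uses data already collected or transferred and needs no further sampling.

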#### **Incidence of anti-PEG binding antibodies**

Number of positive/negative samples will be summarised by visit and listed. Furthermore, plots will be created of incremental recovery according to PEG antibody status at baseline and during the trial. Rules for exclusion of FVIII activity measurements are as defined in the paragraph on: "Pre-dose FVIII activity levels on N8-GP prophylaxis".

### **10.3.4 Interim analyses**

Interim analysis may be performed, if deemed appropriate.

Protocol  
 NN7088-4410

~~CONFIDENTIAL~~

Date:  
 Version:  
 Status:  
 Page:

18 June 2019 | **Novo Nordisk**  
 2.0  
 Final  
 58 of 86

#### 10.4 Pharmacokinetic and/or pharmacodynamic modelling

Data from the trial may be used for exploratory pharmacokinetic and/or pharmacodynamic analysis as needed.

#### 10.5 Additional efficacy related tables/figures/listings

Post-dose activity measurements will be modelled and presented in the same forms as pre-dose activity measurements, see section on “Pre-dose FVIII activity levels on N8-GP prophylaxis”.

Incremental recovery is defined as post-dose FVIII activity minus pre-dose FVIII activity and divided by the administered dose. Incremental recovery will be summarised by visit and listed.

#### 10.6 Additional safety related tables/figures/listings

All safety parameters not addressed above such as laboratory parameters, vital signs and physical examinations will be summarised by visit.

Laboratory reference ranges and abnormal laboratory values will be listed.

Furthermore, the following safety related output will be created.

#### Frequency of adverse events that are reported within the system organ classes nervous system, psychiatric, hepatic and renal disorders

Will be summarised and listed.

#### Changes in laboratory assessments, including hepatic and renal function parameters

Individual profiles of laboratory parameters will be created by age group as plots of parameter values vs. time since first dose in trial.

Estimated glomerular filtration rate (eGFR) in ml/min per 1.73 m^2 will be calculated e.g. using following formula:

$$\text{For } \geq 18 \text{ years of age: Constant} * s\text{-cr}^{-1.154} * \text{age}^{-0.203} * [1.212 \text{ if black or African American}] * [0.742 \text{ if female}], \text{ where constant} = 175 * (88.4^{1.154}) \quad (17)$$

$$\text{For } < 18 \text{ years of age: Constant} * \text{height (cm)} / s\text{-cr}, \text{ where constant} = 0.413 * 88.4 \quad (18)$$

eGFR will also be plotted vs. baseline value.

## 12 Appendices

## Appendix 1 Abbreviations and Trademarks

ABR	Annualised Bleeding Rate
AE	Adverse Event
AESI	Adverse Event of Special Interest
ALT	Alanine Aminotransferase
APCC	Activated Prothrombin Complex Concentrates
BU	Bethesda Units
BW	Body Weight
CHO	Chinese Hamster Ovary
CLAE	Clinical Laboratory Adverse Event
CRF	Case Report Form
CRP	C-reactive protein
CTR	Clinical Trial Report
DCF	Data Clarification Form
DFU	Direction for Use
DRE	Disease Related Event
DUN	Dispensing Unit Number
ECG	Electrocardiogram
eCRF	Electronic Case Report Form
eGFR	Estimated Glomerular Filtration Rate
EMA	European Medicines Agency
EoT	End of Trial
FAS	Full Analysis Set
FDA	U.S. Food and Drug Administration
FDAAA	FDA Amendments Act
FFP	Fresh Frozen Plasma
FPFV	First Patient First Visit
FIX	Coagulation Factor IX
FVIII	Coagulation Factor VIII
FU	Follow-Up

Protocol  
 NN7088-4410

~~CONFIDENTIAL~~

Date:  
 Version:  
 Status:  
 Page:

18 June 2019  
 2.0  
 Final  
 64 of 86

**Novo Nordisk**

GCP	Good Clinical Practice
Hemo-SAT	Haemophilia Satisfaction Survey
HCP	Host Cell Protein
HIV	Human Immunodeficiency Virus
IB	Investigator's Brochure
ICH	International Council for Harmonisation
ICMJE	International Committee of Medical Journal Editors
IEC	Independent Ethics Committee
IgE	Immunoglobulin E
IgG	Immunoglobulin G
IMP	Investigational Medicinal Product
IRB	Institutional Review Board
i.v.	Intravenous
IWRS	Interactive Web Response System
LAR	Legally Acceptable Representative
LPLV	Last Patient Last Visit
MIDF	Monitor-Initiated Discrepancy Form
N8-GP	Turoctocog Alfa Pegol
NIMP	Non-Investigational Medical Product
PCD	Primary Completion Date
pd-aPCC	Plasma-Derived Activated Prothrombin Complex Concentrates
pd-PCC	Plasma-Derived Prothrombin Complex Concentrates
PEG	Polyethylene Glycol
PRO	Patient Reported Outcome
rFVIIa	Activated Recombinant Factor VII
rFVIII	Recombinant Factor VIII
SAE	Serious Adverse Event
SAP	Statistical Analysis Plan
SUSAR	Suspected Unexpected Serious Adverse Reaction
TMM	Trial Materials Manual

Protocol  
NN7088-4410

~~CONFIDENTIAL~~

Date: 18 June 2019 | **Novo Nordisk**  
Version: 2.0  
Status: Final  
Page: 65 of 86

V1, V2...	Visit 1, Visit 2 etc
WFH	World Federation of Haemophilia

## Appendix 2 Clinical laboratory tests

The tests detailed in [Table 12-1](#) will be performed by the central laboratory.

Table 12-1 Protocol-required safety laboratory assessments

Laboratory assessments	Parameters
Haematology	
 
• Haemoglobin
 
• Leucocytes
 
• Thrombocytes
 

Biochemistry	
 
• Alanine Aminotransferase (ALT)
 
• Bilirubin
 
• Creatinine
 
• Urea
 
• C-reactive protein (CRP)
 

Coagulation parameters	
 
• Lupus anticoagulant
 
• von Willebrand factor
 

FVIII activity	
 
• Pre-dose FVIII activity level (trough)
 
• Post-dose FVIII activity level (recovery)
 

Antibodies	
 
• FVIII inhibitors
 
• Anti N8-GP antibodies
 
• Anti PEG antibodies
 

Antibodies (in case of severe allergic reactions)	
 
• FVIII activity
 
• FVIII inhibitors
 
• anti-N8-GP antibodies
 
• anti-PEG antibodies
 
• anti-CHO-HCP antibodies
 
• Tryptase (in case of systemic reactions)
 
• IgE against N8-GP and optional against CHO-HCP
 

Confirmatory/suspicion of inhibitor	
 
• FVIII inhibitors
 
• Anti N8-GP antibody
 
• Anti PEG antibodies
 
• FVIII activity
 
• Lupus anticoagulant
 

Inhibitor follow-up visit	
 
• Lupus anticoagulant
 

Urinalysis	
 
• Albumin/creatinine ratio
 

Human biosamples for retention	
 
• further characterisation if needed (Appendix 7)
 

Local laboratory results are only required in the event of major surgery where the central laboratory results are not available in time for treatment evaluation. If a local sample is required, a sample for central laboratory analysis must be obtained at the same time.

Protocol  
NN7088-4410

~~CONFIDENTIAL~~

Date:  
Version:  
Status:  
Page:

18 June 2019  
2.0  
Final  
67 of 86

**Novo Nordisk**

Additional tests may be performed at any time during the trial as determined necessary by the investigator or required by local regulations. Only laboratory samples specified in the protocol should be sent to the central laboratory for analysis; if additional laboratory sampling is needed, e.g. to follow up on AEs, this must be done at a local laboratory.

The laboratory equipment may provide analyses not requested in the protocol but produced automatically in connection with the requested analyses according to specifications in the laboratory standard operating procedures. Such data will not be transferred to the trial database, but abnormal values will be reported to the investigator.

The investigator must review all laboratory results for concomitant illnesses and AEs. Laboratory samples will be destroyed no later than at end of trial or no later than at finalisation of the clinical trial report.

Human biosamples for retention will be stored as described in [Appendix 7](#).

## Appendix 3 Trial governance considerations

### 1) Regulatory and ethical considerations

This trial will be conducted in accordance with the protocol and with the following:

- Consensus ethical principles derived from international guidelines including the Declaration of Helsinki and applicable ICH Good Clinical Practice (GCP) Guideline
- Applicable laws and regulations
- The protocol, informed consent form, IB (as applicable) and other relevant documents (e.g. advertisements), must be submitted to an IRB/IEC and reviewed and approved by the IRB/IEC before the trial is initiated.
- Regulatory authorities will receive the clinical trial application, protocol amendments, reports on SAEs, and the clinical trial report according to national requirements.
- Any amendments to the protocol will require IRB/IEC approval before implementation of changes made to the trial design, except for changes necessary to eliminate an immediate safety hazard to trial patients.
- Before a trial site is allowed to start screening patients, written notification from Novo Nordisk must be received.
- The investigator will be responsible for:
  - Providing written summaries of the status of the trial annually or more frequently in accordance with the requirements, policies, and procedures established by the IRB/IEC and/or regulatory authorities
  - Notifying the IRB/IEC of SAEs or other significant safety findings as required by IRB/IEC procedures
  - Providing oversight of the conduct of the trial at the site and adherence to requirements of ICH guidelines, the IRB/IEC, and all other applicable local regulations
  - Ensuring submission of the clinical trial report (CTR) synopsis to the IRB/IEC.

### 2) Financial disclosure

Investigators and sub-investigators will provide Novo Nordisk with sufficient, accurate financial information as requested to allow Novo Nordisk to submit complete and accurate financial certification or disclosure statements to the appropriate regulatory authorities. Investigators are responsible for providing information on financial interests during the course of the trial and one year after completion of the trial.

For US trial sites: verification under disclosures per Code of Federal Regulations (CFR) of Financial Conflict of Interest.

Protocol  
NN7088-4410

~~CONFIDENTIAL~~

Date:  
Version:  
Status:  
Page:

18 June 2019  
2.0  
Final  
69 of 86

**Novo Nordisk**

### 3) Informed consent process

The investigator or his/her representative will explain the nature of the trial to the patient and/or the patient's LAR and answer all questions regarding the trial. The investigator must ensure the patient ample time to come to a decision whether or not to participate in the trial.

Patients must be informed that their participation is voluntary. Patients or their LAR will be required to sign and date a statement of informed consent that meets the requirements of local regulations, ICH guidelines , Declaration of Helsinki  and the IRB/IEC or trial site.

The medical record must include a statement that written informed consent was obtained before any trial related activity and the date when the written consent was obtained. The authorised person obtaining the informed consent must also sign and date the informed consent form before any trial related activity.

The responsibility of seeking informed consent must remain with the investigator, but the investigator may delegate the task of informing to a medically qualified person, in accordance with local requirements.

Patients and/or their LAR must be re-consented to the most current version of the informed consent form(s) during their participation in the trial. A copy of the informed consent form(s) must be provided to the patient or the patient's LAR.

If the minor reaches legal age while participating in the trial and has only signed an age specific informed consent/assent form, the patient has to re-consent to the informed consent form signed by the patient's LAR.

### Long-term storage of human samples

If allowed according to local law patient will be asked to sign a consent that addresses long-term storage of human samples and/or the use of samples for optional exploratory research. The objectives of the exploratory research must be explained to each patient.

